Appendix 5 Contraceptive guidance and collection of pregnancy information

It must be recorded in the CRF whether female subjects are of childbearing potential.

Definitions

Woman of Childbearing Potential (WOCBP)

A woman is considered fertile following menarche and until becoming postmenopausal unless permanently sterile.

Women in the following categories are not considered WOCBP

- 1. Premenarcheal
- **2.** Premenopausal female with one of the following:
 - Documented hysterectomy
 - Documented bilateral salpingectomy
 - Documented bilateral oophorectomy

Note: Documentation can come from the site personnel's review of subject's medical records, medical examination or medical history interview.

- 3. Postmenopausal female
 - A postmenopausal state is defined as no menses for 12 months without an alternative
 medical cause. A high Follicle Stimulating Hormone (FSH) level in the postmenopausal
 range may be used to confirm a postmenopausal state in women not using hormonal
 contraception or Hormonal Replacement Therapy (HRT). However, in the absence of 12
 months of amenorrhea, a single FSH measurement is insufficient.
 - Females on HRT and whose menopausal status is in doubt will be required to use one of the
 non-hormonal highly effective contraception methods if they wish to continue their HRT
 during the trial. Otherwise, they must discontinue HRT to allow confirmation of
 postmenopausal status before trial enrolment.

Contraception guidance

Female subjects:

Female subjects of childbearing potential are eligible to participate if they agree to use methods of contraception consistently and correctly as described in table(s) below:

Table 6 Highly effective contraceptive methods

Highly effective contraceptive methods that are user dependent ^a

Failure rate of <1% per year when used consistently and correctly.

- Combined (oestrogen and progestogen containing) hormonal contraception associated with inhibition of ovulation b
- oral

Page:

63 of 68

- intravaginal
- transdermal

Progestogen only hormonal contraception associated with inhibition of ovulation

- oral
- injectable

Highly effective methods that are user independent a

Implantable progestogen only hormonal contraception associated with inhibition of ovulation b

- Intrauterine Device (IUD)
- Intrauterine hormone-releasing System (IUS)
- Bilateral tubal occlusion

Vasectomised partner

A vasectomised partner is a highly effective contraception method provided that the partner is the sole male sexual partner of the WOCBP and the absence of sperm has been confirmed. If not, an additional highly effective method of contraception should be used.

Sexual abstinence

Sexual abstinence is considered a highly effective method only if defined as refraining from heterosexual intercourse during the entire period of risk associated with the trial product. The reliability of sexual abstinence needs to be evaluated in relation to the duration of the trial and the preferred and usual lifestyle of the subject.

Notes:

^aTypical use failure rates may differ from those when used consistently and correctly. Use should be consistent with local regulations regarding the use of contraceptive methods for subjects participating in clinical trials.

^bHormonal contraception may be susceptible to interaction with the trial product, which may reduce the efficacy of the contraceptive method. In this case, two highly effective methods of contraception should be utilised during the treatment period and for at least 7 days after the last dose of trial product.

Table 7 Acceptable effective contraceptive methods

Acceptable effective contraceptive methods^a

Failure rate of >1% per year when used consistently and correctly

- Progestogen-only oral hormonal contraception, where inhibition of ovulation is not the primary mode of action.
- Male or female condom with or without spermicide
- Cap, diaphragm or sponge with spermicide

Note:

^aTypical use failure rates may differ from those when used consistently and correctly. Use should be consistent with local regulations regarding the use of contraceptive methods for subjects participating in clinical trials.

Pregnancy testing

- WOCBP should only be included after a negative highly sensitive serum pregnancy test.
- Additional urine pregnancy testing should be performed at monthly intervals during the treatment period, if required locally.
- Pregnancy testing should be performed whenever a menstrual cycle is missed or when pregnancy is otherwise suspected.

Protocol		Date:		Novo Nordisk
Trial ID: NN1250-4419	CONFIDENTIAL	Version:	3.0	
		Status:	Final	
		Page:	64 of 68	

Collection of pregnancy information

Female subjects who become pregnant

- Investigator will collect pregnancy information on any female subject, who becomes pregnant while participating in this trial.
- Information will be recorded on the appropriate form and submitted to Novo Nordisk within 14 calendar days of learning of a subject's pregnancy.
- Subject will be followed to determine the outcome of the pregnancy. The investigator will collect follow-up information on subject and neonate, which will be forwarded to Novo Nordisk. Generally, follow-up will not be required for longer than 1 month beyond the delivery date.
- Any termination of pregnancy will be reported, regardless of foetal status (presence or absence of anomalies) or indication for procedure.
- While pregnancy itself is not considered to be an AE or SAE, any pregnancy complication or elective termination of a pregnancy will be reported as an AE or SAE.
- A spontaneous abortion is always considered to be an SAE and will be reported as such.
- Any SAE occurring as a result of a post-trial pregnancy which is considered
 possibly/probably related to the trial product by the investigator will be reported to Novo
 Nordisk as described in Appendix 4. While the investigator is not obligated to actively seek
 this information in former subjects, he or she may learn of an SAE through spontaneous
 reporting.

Any female subject who becomes pregnant while participating in the trial **will discontinue** trial product.

Page:

65 of 68

Appendix 6 Technical complaints: Definition and procedures for recording, evaluation, follow-up and reporting

Technical complaint definition

• A technical complaint is any written, electronic or oral communication that alleges product (medicine or device) defects. The technical complaint may be associated with an AE, but does not concern the AE itself.

Examples of technical complaints:

- Problems with the physical or chemical appearance of trial products (e.g. discoloration, particles or contamination).
- Problems with packaging material including labelling.
- Problems related to medical devices (e.g. to the injection mechanism, dose setting mechanism, push button or interface between the pen-injector and the needle).

Time period for detecting technical complaints

• All technical complaints, which occur from the time of receipt of the product at trial site until the time of the last usage of the product, must be collected for products predefined on the technical complaint form.

Reporting of technical complaints to Novo Nordisk

Contact details (fax, e-mail and address) for Customer Complaint Center – refer to Attachment I

Technical complaints must be reported on a separate technical complaint form:

- 1. One technical complaint form must be completed for each affected DUN
- 2. If DUN is not available, a technical complaint form for each batch, code or lot number must be completed

Timelines for reporting of technical complaints to Novo Nordisk

The investigator must complete the technical complaint form in the CRF within 24 hours if related to an SAE. All other technical complaints with or without associated AEs within 5 calendar days. If the CRF is unavailable or when reporting a technical complaint that is not subject related, the information must be provided on a paper form by fax, email or courier to Customer Complaint Center, Novo Nordisk, within the same timelines as stated above. When the CRF becomes available again, the investigator must enter the information on the technical complaint form in the CRF.

Follow-up of technical complaints

The investigator is responsible for ensuring that new or updated information will be recorded on the originally completed form.

Collection, storage and shipment of technical complaint samples

The investigator must collect the technical complaint sample and all associated parts that were packed in the same DUN and notify the monitor within 5 calendar days of obtaining the sample at trial site. The sample and all associated parts must be sent as soon as possible to Customer Complaint Center, Novo Nordisk, together with a copy of the completed technical complaint form. The technical complaint sample should contain the batch, code or lot number and, if available, the DUN. If the technical complaint sample is unobtainable, the reason must be stated on the technical complaint form. If several samples are shipped in one shipment, the sample and the corresponding technical complaint form should be kept together.

Storage of the technical complaint sample must be done in accordance with the conditions prescribed for the product.

Reporting of technical complaints for Novo Nordisk products not included in technical complaint form

Technical complaints on Novo Nordisk products not included in the technical complaint form should be reported to local Novo Nordisk affiliate with a reference to trial ID.

Protocol		Date:	01 June 2018	Novo Nordisk
Trial ID: NN1250-4419	CONFIDENTIAL	Version:	3.0	
		Status:	Final	
		Page:	66 of 68	

Appendix 7 Country-specific requirements

- For Poland: Novo Nordisk carries liability for the trial exclusively in the scope defined by
 the applicable laws and in particular by the Civil Code and the Pharmaceutical Law dated 6
 September 2001 (uniform version Journal of Laws of 2008 No.45 item 271 with
 amendments). In order to support potential claims for liability attributable to the Trial, Novo
 Nordisk and investigator are covered by Insurance Policy issued according to applicable
 Polish law.
- For Slovakia: It is necessary that the Trial Sponsor covers all costs for treatment of the disease studied. It is necessary to cover the whole diabetes medication, payment for insulin, OADs listed in Inclusion criteria no. 5 and rescue medication, if used.

| Protocol | | Date: | 01 June 2018 | Novo Nordisk | Version: | 3.0 | Status: | Final | Page: | 67 of 68 | |

Appendix 8 Titration guideline

Titration guidelines have been developed, providing recommended dose adjustments at different PG levels to ensure that subjects receive an optimal treatment. However, it is recognised that insulin treatment should be individualised and the specific titration algorithms may not be applicable in certain clinical situations. Hence, it is important that other information, such as symptoms of hypo/hyperglycaemia, previous response to dose adjustments, other glucose measurements and other indicators of the subject's level of glycaemic control, is taken into consideration when decisions on dosing are made. The investigator is responsible for the treatment of the subjects and can therefore overrule the guidelines to avoid safety hazards.

Initiation of trial products

IGlar 100U/mL and IDeg should be injected subcutaneously into the thigh, upper arm (deltoid area) or the abdomen. The chosen region should be the same throughout the trial for each trial products. Rotation of injection sites within a given region is recommended.

Both IMPs should be taken once daily any time of the day, but at the same time every day. At randomisation (Visit 3) subjects will initiate treatment according to local label for the relevant IMP. At cross-over (Visit 21) the subjects should switch according to local label for the relevant IMP.

Dose adjustment of trial products during the trial

After randomisation the insulin dose will be evaluated and possibly adjusted once weekly by the investigator in connection with the scheduled visits/phone contacts during the titration periods. The dose adjustment will be based on the mean of three fasting SMPG values measured on two days prior to titration and on the day of the visit/contacts according to Table 8. If one of the SMPG values is below target (<3.9 mmol/L or 70 mg/dL) then dose adjustment will be based on the lowest SMPG values according to Table 9.

If one or more SMPGs values are missing, the adjustment should be performed on the remaining SMPG value(s).

Table 8 Increase of insulin dose

Mean pre-breakfast SMPG values		Increase of basal insulin	
		dose	
mmol/L	mg/dL	U	
3.9 - 5.0	70 – 90	No adjustment	
5.1 - 7.0	91 – 126	+ 2	
7.1 - 8.0	127 – 144	+ 4	
8.1 - 9.0	145 – 162	+ 6	
> 9.0	> 162	+ 8	

Protocol		Date:	01 June 2018	Novo Nordisk
Trial ID: NN1250-4419	CONFIDENTIAL	Version:	3.0	
		Status:	Final	
		Page:	68 of 68	

Table 9 Reduction of insulin dose

Lowest pre-breakfast SMPG value		Reduction of basal insulin dose	
mmol/L	mg/dL	U	
3.1 – 3.8	56 – 69	- 2	
<3.1	< 56	- 4	

Deviations from the algorithm

It is recommended that the algorithm is followed. However, it is also important that the decision to adjust insulin doses is based on all relevant information. A reason for deviating from the algorithm should be entered into the eCRF by the investigator as applicable.

Data surveillance

Surveillance of titration data will be performed centrally by Novo Nordisk in an unbiased or, if possible, a blinded manner. The data will be reviewed and significant changes from the titration algorithm will be followed up.

It is important that data regarding dose titration is entered into the applicable system. If delays occur, action cannot be taken in due time before the subject's next site visit/phone contact. The aim is to reduce the time periods in which a subject may receive suboptimal treatment.

The titration data should be reviewed by Novo Nordisk within 24 hours (on workdays). The reviewer may contact the investigator by e-mail or phone to clarify reasons for deviation or to request entry of missing data. When the investigator receives an inquiry, a response should be received at Novo Nordisk within 24 hours (on workdays).

In addition, Novo Nordisk will monitor changes in HbA1c. Novo Nordisk may visit or phone sites to discuss progress in glycaemic control and titration of individual subjects.

Insulin degludec (Tresiba®)		Date:	04 May 2020	Novo Nordisk
Trial ID: NN1250-4419	CONFIDENTIAL	Version:	1.0	
Clinical Trial Report		Status:	Final	

23 January 2020 Novo Nordisk 2.0 Final 3 of 17

List of abbreviations

| ADA | American Diabetes Association |
|--------|-------------------------------|
| CGM | continuous glucose monitoring |
| FGM | flash glucose monitoring |
| HbA1c | glycated haemoglobin |
| LLOQ | lower limit of quantification |
| OAD(s) | oral anti-diabetic drug(s) |
| OD | once daily |
| PP | per protocol |
| PYE | person years of exposure |
| SAP | statistical analysis plan |
| T2DM | type 2 diabetes mettilus |
| ULOQ | upper limit of quantification |

CONFIDENTIAL

Date: Version: Status: Page: 23 January 2020 2.0 Final 4 of 17

Novo Nordisk

1 Introduction

1.1 Trial information

Objectives, estimand and endpoints:

Primary, secondary and explorative objective(s)

The primary objective is to compare the effect on glycaemic control of IDeg versus IGlar 100U/m in a population of T2DM subjects with or without OADs, using FGM.

Estimand

The primary estimand is the treatment difference between IDeg and IGlar 100U/mL with respect to percent time spent in glycaemic target range for all randomised subjects that can use the FGM sensor and adhere to at least 18 weeks of treatment on both insulins. An intercurrent event for the primary estimand include lack of effect from any of the insulins leading to a need for initiation of other diabetes medication(s). As described in section 8.1 in the protocol, treatment intensification may result in trial discontinuation. The primary estimand will handle these intercurrent events as withdrawals and only use data from completers. The primary estimand is the principle stratum direct effect for the population of completers.

Primary endpoint

Percentage of time spent in glycaemic target range 70-180 mg/dL (3.9–10.0 mmol/L) both inclusive, during the 2-week maintenance period using FGM (Visit 19-21 (week 16-17) and Visit 37-39 (week 34-35)).

Supportive secondary endpoints

- Percentage of time spent in tight glycaemic target range 70-140 mg/dL (3.9–7.8 mmol/L) both inclusive, during the 2-week maintenance periods using FGM (Visit 19-21 (week 16-17) and Visit 37-39 (week 34-35)).
- Percentage of time spent in nocturnal glycaemic target range 70-140 mg/dL (3.9-7.8 mmol/L) both inclusive, in the nocturnal period (00:01 am 05:59 am both inclusive) during the 2-week maintenance periods using FGM (Visit 19-21 (week 16-17) and Visit 37-39 (week 34-35)).
- HbA1c (% and mmol/mol) after two weeks of maintenance periods (Visit 19-21 (week 16-17) and Visit 37-39 (week 34-35)).
- Mean glucose levels (mg/dL and mmol/L) during the 2-week maintenance periods using FGM (Visit 19-21 (week 16-17) and Visit 37-39 (week 34-35)).

Exploratory endpoints

| Statistical Analysis Plan | | Date: | 23 January 2020 | Novo Nordisk |
|----------------------------|--------------|----------|-----------------|--------------|
| Trial ID: 1250-4419 | CONFIDENTIAL | Version: | 2.0 | |
| UTN: 1111-1203-0580 | CONFIDENTIAL | Status: | Final | |
| EudraCT no: 2017-004047-20 | | Page: | 5 of 17 | |

- Glycaemic variability calculated as standard deviation (mg/dL and mmol/L) and coefficient of variation (%) of glucose levels during the 2-week maintenance treatment using FGM(Visit 19-21 (week 16-17) and Visit 37-39 (week 34-35)).
- Mean insulin dose (IU) during the 2-week maintenance treatment period (Visit 19-21 (week 16-17) and Visit 37-39 (week 34-35)).
- Percentage of time spent in the hypoglycaemia alert range (Level 1) 54-69 mg/dL (3.0-3.8 mmol/L) both inclusive, during the 2-week maintenance periods using FGM (Visit 19-21 (week 16-17) and Visit 37-39 (week 34-35)).
- Percentage of time spent in the clinically significant hypoglycaemic range (Level 2) <54mg/dL (<3.0 mmol/L) during the 2-week maintenance periods using FGM (Visit 19-21 (week 16-17) and Visit 37-39 (week 34-35)).
- Number of clinically significant hypoglycaemic episodes (Level 2) <54mg/dL (<3.0 mmol/L) for at least 15 minutes during the 2-week maintenance periods using FGM (Visit 19-21 (week 16-17) and Visit 37-39 (week 34-35)).
- Number of clinically significant hypoglycaemic episodes (Level 2) <54mg/dL (<3.0 mmol/L) for at least 15 minutes in the nocturnal period (00:01-05:59 AM, both inclusive) during the 2-week maintenance periods using FGM (Visit 19-21 (week 16-17) and Visit 37-39 (week 34-35)).

Trial design:

This trial is a 41-week, randomised, cross-over, open-label, multi-center, active controlled trial comparing the effect of insulin IDeg versus insulin IGlar 100U/mL, with or without OADs in subjects with type 2 diabetes using flash glucose monitoring.

The trial includes a screening visit (Visit 1), followed by a 2-week run-in period for eligibility assessment in regards to adherence to FGM requirements. At randomisation (Visit 3), eligible subjects will be randomised 1:1 into one of two treatment periods receiving either IDeg or IGlar 100U/mL. Each treatment period consist of a 16-week titration period followed by a 2-weeks maintenance period where subjects will wear the FreeStyle Libre Pro Sensor. After the first titration and maintenance period the subject will switch to the other trial product, with dose adjustment according to local label, performing the same assessments as in the first treatment period (16-week titration period followed by a 2-weeks maintenance period).

The follow-up period is 1 week.

EudraCT no: 2017-004047-20

2.0

[figure not shown]

Figure 1 **Trial Design**

Further details

For further details on trial design and endpoints please see the NN1250-4419 protocol version 3.0.

1.2 Scope of the statistical analysis plan

This SAP is based on the NN1250-4419 protocol, version 3.0.

2 Statistical considerations

2.1 Sample size determination

The sample size calculation is based on the primary objective for the primary estimand and the primary endpoint of the trial, and is performed as a paired-sample calculation in terms of the mean and standard deviation of the within pair difference within the PP using the paired t-test. Only one previous Novo Nordisk trial using CGM has had a similar design: NN1250-3874 comparing IDeg and IGlar 100U/mL in 24 T1DM subjects using a cross-over design. Regarding time in glycaemic target range (70-180 mg/dL) during the full 24 hours of the day, the within pair difference between IDeg and IGlar 100U/mL had a mean of 0.39 hours and a standard deviation of 2.3. Two previous Novo Nordisk studies have used CGM in T2DM subjects in parallel arm designs, NN1250-3579 and NN1250-3668. However, CGM technology used in those two T2DM trials is outdated compared to the devices used in the current trial, and they are therefore deemed irrelevant as to

| Statistical Analysis Plan | | Date: | 23 January 2020 | Novo Nordisk |
|----------------------------|--------------|----------|-----------------|--------------|
| Trial ID: 1250-4419 | CONFIDENTIAL | Version: | 2.0 | |
| UTN: 1111-1203-0580 | CONFIDENTIAL | Status: | Final | |
| EudraCT no: 2017-004047-20 | | Page: | 7 of 17 | |

guidance on expected difference between the two treatments in this trial. The results from the NN1250-3874 trial are used for sample size calculation despite the differences from the present trial, i.e. indication and length of maintenance treatment. A conservative standard deviation of 2.6 is used. To detect a mean difference of 0.39 with 85% power with a standard deviation of 2.6 based on a paired t-test and 1:1 randomisation requires 401 subjects included in the PP. See Table 3 for sample sizes based on a range of standard deviation and for mean differences of 0.39 and 0.5

| Effect | | | | |
|--------|------|------|--|--|
| SD | 0.39 | 0.50 | | |
| 2.0 | 239 | 146 | | |
| 2.3 | 315 | 192 | | |
| 2.6 | 401 | 245 | | |

Sample size is computed for 1:1 randomisation and 85% power. SD: standard deviation. respectively.

Table 1 Sample size and power for various standard deviations and effects

2.2 Definition of analysis sets

The full analysis set is all subjects randomised at Visit 3. The safety analysis set is all subjects that are randomised and treated with at least one dose of trial drug after randomisation.

The PP analysis set consists of subjects that stay on assigned treatment until and complete FGM assessment at visits 21 and 39 respectively. Complete FGM assessment is specified as subjects having at least 70% of two weeks FGM measurements per maintenance period (2 * 960 measurements). FGM measurements from the first 24 hours of each fitted sensor are disregarded. All endpoint analysis will be performed on the PP analysis set.

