5.2 Subject and trial completion

Approximately 674 subjects will be screened to achieve 472 subjects randomly assigned to trial product.

Approximately 502 subjects are planned to be included in the run-in period.

Trial period completion for a subject:

Trial period completion is defined as when the randomised subject has completed the final scheduled visit ('end of trial' according to the flowchart).

'Date of trial completion' is the date the subject completed the final scheduled visit.

Treatment period completion for a subject:

Treatment period completion is defined as when the randomised subject has received the required treatment, and attended the 'end of treatment' visit according to the flowchart.

The treatment period 1 starts at Visit 3 and is defined as when the randomised subject has received the required treatment for at least 18 weeks and attended Visit 21 according to the flowchart.

The treatment period 2 starts at Visit 21 and is defined as when the randomised subject has received the required treatment for at least 18 weeks and attended Visit 39 according to the flowchart.

Required treatment:

Completion of both treatment periods is required for contribution to the analysis. Only the data from subjects completing 16 weeks of titration and 2 weeks of maintenance wearing the FreeStyle Libre Pro device, with both trial products, will be used in the outcome analyses.

Protocol
Trial ID: NN1250-4419

CONFIDENTIAL
Date: 01 June 2018 Version: 3.0
Status: Final Page: 18 of 68

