10.3.1 Primary endpoint

The primary endpoint is the percentage of time spent in glycaemic target range (70-180 mg/dL (3.9-10.0 mmol/L), both inclusive) during the 2-week maintenance period. The FreeStyle Libre Pro device stores four measurements per hour and a subject with complete data will contribute with 14*24*4=1344 measurements from each 2-week period. The analysis will discard data from the

Protocol Trial ID: NN1250-4419	CONFIDENTIAL	Date: Version: Status:	01 June 2018 3.0 Final	Novo Nordisk
		Page:	39 of 68	

first 24 hours as per communication with the vendor and so subjects with complete data will contribute with 13*24*4=1248 glucose recordings. The number of recorded measurements may be smaller for various reasons for subjects in the PP analysis set. Following ADA criteria we will demand that at least 70% of two weeks FGM measurements, corresponding to 10 days of FGM data, must be available for subjects to be included in the analysis. The percentage of time spent in glycaemic target range will be calculated as the number of recorded measurements in glycaemic target range (70-180 mg/dL (3.9-10.0 mmol/L), both inclusive) divided by the total number of recorded measurements.

The primary estimand will be estimated by the primary endpoint analysed in a linear mixed model with treatment and period as fixed effects, subject as a random effect and with an unstructured residual variance matrix.

Using the unblinded data and before DBL, visual tools will be used to determine whether the data, including the primary endpoint, are normally distributed. If it is then found that the data are not normal, an appropriate transformation will be performed and this will be documented in a SAP or the DBL minutes.

Superiority of IDeg OD compared to IGlar 100U/mL OD with respect to percentage of time spent in glycaemic target range will be considered confirmed if non-inferiority is confirmed and the lower limit of the two-sided 95% confidence interval of the difference (IDeg OD - IGlar 100U/mL OD) is entirely above zero or equivalently if the p-value for the one-sided test of

H0: $D \le 0\%$ against HA: D > 0%

is smaller than 2.5%, where D is the estimated mean difference of time spent in glycaemic target range (IDeg OD - IGlar 100U/mL OD). As such, a fixed hierarchical testing procedure will be applied, which will effectively adjust for multiple testing.

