is smaller than 2.5%, where D is the estimated mean difference of time spent in glycaemic target range (IDeg OD - IGlar 100U/mL OD). As such, a fixed hierarchical testing procedure will be applied, which will effectively adjust for multiple testing.

Non-inferiority will be evaluated by comparing the lower limit of the two-sided 95% confidence interval for the difference between IDeg and IGlar 100U/mL to a non-inferiority margin of 0.2h/24h (0.83%). If the lower CI limit is above -0.83%, non-inferiority will be considered established. The two-tailed p-value will be reported for the test of superiority.

Missing data due to intercurrent events such as trial discontinuation is not relevant since the primary estimand is based on the PP analysis set.

A sensitivity analysis will be performed to account for heteroscedasticity due to a varying number of FGM readings within the 70% demand. Specifically, the primary endpoint will be analysed by applying the weight statement in the proc mixed procedure with weights calculated as the square root of the total number of FGM readings.

An additional sensitivity analysis will be performed where all subjects who have FGM readings for at least seven consecutive days will be included. Weighting will be performed as described previously.

Following specifications from the vendor the accuracy of the FGM measurements can be influenced by intake of either ascorbic or/and salicylic acid [1]. The level of consequence depends on the amount of the interfering substance active in the body [1]. Due to the trial design, doses of non-

| Statistical Analysis Plan | | Date: | 23 January 2020 | Novo Nordisk |
|----------------------------|--------------|----------|-----------------|--------------|
| Trial ID: 1250-4419 | CONFIDENTIAL | Version: | 2.0 | |
| UTN: 1111-1203-0580 | CONFIDENTIAL | Status: | Final | |
| EudraCT no: 2017-004047-20 | | Page: | 9 of 17 | |

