diabetic concomitant medications are not collected, and it is hereby not possible to identify high risk subjects. A sensitivity analysis will be performed where all FGM measurements, for subjects in the PP analysis set, coinciding with intake of ascorbic and/or salicylic acid, will be excluded. Taking washout periods of both ascorbic and salicylic acid (also applicable for multivitamins including ascorbic acid) into consideration, FGM measurements overlapping the start-to-end dates of intake of either drug + 1 day will be omitted in the analysis. This will result in partial or complete FGM profiles being disregarded. Weighting will be applied as described previously to account for heteroscedasticity due to a varying number of FGM readings

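### Does the SAP's rule that every endpoint analysis uses the per-protocol set cancel its own seven-day sensitivity analysis?

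*SAP*

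**What the plan says.** SAP 2.2 builds the PP set from two conditions: the subject remains on the assigned insulin up to Visits 21 and 39, and the glucose monitoring is complete, meaning "at least 70% of two weeks FGM measurements per maintenance period (2 * 960 measurements". The first 24 hours of every fitted sensor do not count. The section ends with the general sentence "All endpoint analysis will be performed on the PP analysis set". SAP 3.1 records that both the 960 figure and this sentence are additions to protocol 10.2.

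SAP 2.3 then lists three sensitivity analyses for the primary endpoint:

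- A weighted analysis within the 70% requirement, using "weights calculated as the square root of the total number of FGM readings".
- An analysis in which "all subjects who have FGM readings for at least seven consecutive days will be included", with the same weighting. No analysis set is named.
- An analysis that drops readings "for subjects in the PP analysis set, coinciding with intake of ascorbic and/or salicylic acid, will be excluded".

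The protocol has related wording. Section 5.2 says "Completion of both treatment periods is required for contribution to the analysis" and that only data from subjects with the full titration and "2 weeks of maintenance wearing the FreeStyle Libre Pro device, with both trial products, will be used in the outcome analyses". Section 10.3.1 sets the 70% rule, "corresponding to 10 days of FGM data, must be available for subjects to be included in the analysis", and two paragraphs of sensitivity analyses later describes the same seven-day analysis.

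**The concern.** The seven-day analysis is the only planned analysis that could bring in subjects who miss the completeness cut-off, so it is the only one that shows whether the cut-off matters. If the closing sentence of SAP 2.2 is taken at face value, those subjects are excluded before the analysis starts. It would then use the PP set or part of it, with the same weights as the first sensitivity analysis, and could tell the reader nothing new about the cut-off.

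The sentence was added deliberately to make the PP definition unambiguous, and no exception was written. The protocol does not obviously rescue the analysis, because its section 5.2 also speaks of two weeks of wear on both products. A second, smaller oddity sits in the same definition: 960 readings is not exactly 70% of two weeks.

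**Working it through.** **Inputs.** Four readings per hour, so 96 per day (SAP 2.3). Two full weeks give 14 × 96 = 1344 readings; with the first day of a single sensor removed, 13 × 96 = 1248 (SAP 2.3). The PP cut-off is 960 per period (SAP 2.2), equated with 10 days (SAP 2.3).

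**The plan's own figure.** 10 × 96 = 960, which reproduces the cut-off. An exact 70% is 0.70 × 1344 = 940.8, or 941 readings, and 960/1344 = 71.4%. The gap is 960 − 941 = 19 readings, or 19 × 15 min = 4.75 h. SAP 2.2 prints 960, and both documents equate 70% with 10 days, so 960 is the operative number and 70% is its rounded description.

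**The two rules compared.** Seven fully recorded days give 7 × 96 = 672 readings, which is 288 below the cut-off. The figure 672 is derived here and not printed in the SAP. The SAP does not say how complete each day must be, so 672 is an illustration and not a firm lower bound.

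**Set logic.** All 2^13 = 8192 whole-day availability patterns over the 13 analysable days of one period were enumerated:

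| Pattern | Count |
|---|---|
| At least 10 days and a seven-day run | 138 |
| At least 10 days, no seven-day run | 240 |
| Seven-day run, fewer than 10 days | 118 |
| Of those 118, left after a literal PP filter | 0 |

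The literal reading therefore does empty the added group. These are counts of possible patterns, not of expected subjects.

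**How many subjects could be involved.** Protocol 9.1.1.3 requires a cumulative 14 days of sensor data, with a new sensor fitted promptly if one falls off. With k sensors, (14 − k) × 96 readings remain: 1248, 1152, 1056 and 960 for k = 1, 2, 3 and 4. A subject handled as the protocol requires thus reaches 960 even with four sensors, if no readings are lost within the wear time. Protocol 10.1 expects nearly all completers to meet the 70% rule. The subjects at stake are departures from that procedure, for example a single sensor worn 8 days and not replaced, which leaves 7 × 96 = 672 readings.

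**Could PP subjects be lost from the seven-day analysis?** Two sensors worn 7 + 7 days leave 6 + 6 analysable days, or 12 × 96 = 1152 readings, with a longest analysable run of six days. Such a subject drops out only if the run is counted after each sensor's first day is discarded. If recorded days are counted and replacement is prompt, the run is about 14 days. The SAP does not choose between these.

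**Reading the sections together.** Three features show which sentence governs:

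- The seven-day paragraph names whom it includes, and that group is wider than the PP set.
- The acid-intake paragraph directly after it restricts itself to PP subjects. That restriction would be redundant if the sentence in SAP 2.2 already bound every analysis without exception.
- SAP 3.4 and 3.5 revisit the seven-day paragraph and keep it alongside the new sentence, changing only its weighting wording and adding the acid-intake analysis after it.

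**The case for a change.** The best case for a change is that intent does not fix a population. Even if an exception is understood, the SAP does not say whether seven days are needed in one period or both, whether staying on treatment to Visits 21 and 39 still applies, how days are counted around a sensor change, or whether PP subjects without a seven-day run stay in. Two programmers could build different sets. SAP 2.3 also provides for a look at unblinded data before database lock, and the wording that would settle the matter costs one clause.

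The gaps are real, and so is the missing exception phrase. They do not amount to a flaw in the plan. A within-subject comparison needs both periods to be informative, and protocol 5.2 requires completion of both for a subject to contribute, so an analyst has a natural default for the first two questions. The other two concern how a few sensor patterns are handled in a supporting analysis and can be settled in the programming specification. The unblinded look is meant for judging normality and choosing a transformation; it is not a route to choosing this population. Nor is the 10-day rule in protocol 10.3.1 in conflict with the seven-day analysis that follows it, since relaxing the primary rule is what a sensitivity analysis is for.

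**Conclusion.** No change to the plan is needed. The general sentence in SAP 2.2 lacks an exception, and read in isolation it would leave the seven-day analysis with nobody to add. Read with SAP 2.3 it does not, because the specific population stated there governs. The 941 versus 960 difference is rounding, with the operative figure printed.

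The effect is confined to one sensitivity analysis. Even on the literal reading, the worst outcome is that this analysis repeats the weighted PP analysis or uses a subset of it. The primary result and the conclusions on non-inferiority and superiority would be the same either way.

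This rests on two assumptions: that the analysts follow the specific wording of SAP 2.3, and that few completers fall below 960 readings in a period. The documents give no count for the second; the 14-day requirement and the stated expectation in protocol 10.1 both point to a small number.
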